7.1 Inclusion Criteria

The subjects must meet the following inclusion criteria:

1. Age 18 years and older
2. Dry tympanic membrane perforation of greater than 3 months duration
3. If female, post-menopausal or sterile, or if she is of child-bearing potential, must have a negative beta-HCG test and must be using an adequate form of birth control such as birth control pills, birth control implants, intrauterine devices (IUDs), diaphragms, or condoms throughout the clinical trial.

7.2 Exclusion Criteria

The presence of any of the following excludes a subject from study enrollment:

1. Active otitis media or chronic otorrhea from the middle ear
2. Subjects receiving radiation therapy, corticosteroids, immunosuppressive agents or chemotherapy
3. Subjects who, at study entry, are taking systemic antibiotics
4. Subjects who are immunosuppressed
5. Subjects experiencing bacterial or viral infection or who may otherwise be febrile
6. Active alcohol or drug abuse within 6 months prior to study entry
7. Significant medical condition that could prevent full participation in the procedures required for the study

8. Not able to complete all study procedures
9. Subjects with known allergies to porcine collagen
10. Subjects who have cholesteatoma mass in the tympanic cavity
11. Subjects whose total perforation cannot be seen by an endoscope
12. Subjects with inadequately controlled diabetes mellitus (HbA1c 6.9% or higher).
HbA1c will be measured at baseline to assure entry criteria are met.
13. Subjects with a history of malignant ear canal tumors within 3 years of screening for eligibility
14. Subjects who are judged by the investigator or sub-investigator(s) to be inappropriate to participate in the study

7.3 Removal of Subjects from Treatment or Assessment

Reasons for permanent discontinuation include the following:

If three treatments do not result in complete closure, subsequent treatments will not be administered if any ear complications occur in the treated ear, including but not limited to, infection, requires other surgery, moderate to severe pain, moderate to severe irritation, clinically significant hearing loss. All subjects will complete all safety follow-up visits.

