- 3) Place a human fibroblast growth factor-2 (FGF-2) soaked pledget of bioabsorbable gelatin sponge larger than the tympanic membrane so the tympanic membrane is completely covered.
- 4) Secure the pledget in place with several drops of fibrin glue.
- 5) After the effects of the topical anesthetic have worn off, if any, the patient is released with the following instructions:
 - a) Avoid violently sniffling or blowing the nose
 - b) Sneeze and cough naturally through the mouth without occluding the mouth with the hand.
 - c) Use cotton balls covered with petroleum jelly on the outer surface when washing the hair and bathing. This is needed to help keep water out of the ear.
 - d) Avoid using a hearing aid in the treated ear.
 - e) Avoid flying, using elevators in tall buildings, and other situations involving substantial changes in air pressure.
 - f) Avoid swimming.

DISCONTINUATION FROM TREATMENT:

Reasons for permanent discontinuation include the following:

If the first treatment does not result in complete closure, subsequent treatments will not be administered if any ear complications occur in the treated ear, including but not limited to infection, moderate to severe pain, moderate to severe irritation, or clinically significant sensorineural hearing loss. All subjects will complete all safety follow up visits.

PRIMARY ENDPOINT:

The tympanic membrane and surrounding structures will be examined every 21-days (+7 days) for up to three visits. Adverse events will be recorded at all visits. Routine laboratory tests will be performed at the screening visit and at the final study visit. Vital signs will be assessed at each study visit and changes in clinical examination findings will be noted.

SECONDARY ENDPOINTS:

- Tympanic membrane perforation closure determined by otoscopic exam and photographic documentation
- Pure-tone and speech discrimination scores as measured by pre- and post-treatment audiograms
- Mobility of the tympanic membrane as measured by tympanometry
- Salvage rate of FGF-2 in patients who fail placebo

STATISTICAL ANALYSIS:

The target enrollment of 75 subjects will provide sufficient power while also accounting for potential retention issues. The primary endpoint is to confirm the efficacy of

FGF-2 in subject with TMR by testing the hypothesis that the rate of subject with complete closure of the TMR will be superior to that placebo.

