5.1 Overall Study Design and Plan Description

This study is a double blinded, placebo controlled phase II study evaluating the efficacy of FGF-2 for the treatment of chronic non-healing tympanic membrane perforations (TMP). The documentation of TM closure will be the main efficacy outcome measure. Pretreatment photographs will document the area of the TM perforation and allow measurement of surface areas of the TMP for comparison of pre- and post-treatment. The study will be divided into two phases, the Randomized Treatment phase (part A), and the Unblinded Crossover phase (part B). In part A of the study, subjects will be randomized 3:1 to receive FGF-2 or placebo treatment up to 3 treatments. Subjects that fail three study treatments will move on to part B of the study. Subjects who received placebo in part A and failed three placebo treatments will crossover to receive unblinded FGF-2 for up to 3 treatments. Subjects who received FGF-2 in part A and failed three experimental treatments will not have additional FGF-2 treatment, and will move on to study follow up.

The primary outcome for the study will be to determine the TMP closure efficacy of FGF-2 and placebo, with up to 3 treatments each. The OBD was determined to be 100 μ g of FGF-2 per 1 mL with an estimated dose of about 20 μ g in 0.2ml in prior studies by [name] (Kanemaru et al., 2011).

Secondary outcomes for the study include: (1) Determination of the time to closure of tympanic membrane perforation, (2) Measurement of changes in pure-tone and speech discrimination scores, (3) Determination mobility of tympanic membrane as measured by tympanometry, and (4) Observation of salvage rate of FGF-2 treatment in subjects who failed placebo treatment.

If both ears are affected by chronic perforation, only one ear will be initially enrolled in the study and receive treatment. The ear with the more significant symptoms will be the one enrolled in the study (i.e., greater conductive hearing loss). The non-study ear will not be enrolled or undergo additional treatments during the study period.

- 1) In an outpatient examination, the subject will be confirmed to have a tympanic membrane perforation by microscopic otoscopy and that no active infection and/or inflammation is present. Then a cotton ball soaked in 4% lidocaine jelly will be inserted with micro alligator forceps directly to the surface of the tympanic membrane under microscopic visualization.

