- 2) After 15 minutes, the lidocaine infused cotton ball will be removed and the edge of the perforation roughened with a micropick to remove the epithelium circumferentially around the perforation edge.
- 3) A human fibroblast growth factor-2 (FGF-2) soaked pledget (approximately 20 µg in 0.2ml) of bioabsorbable gelatin sponge slightly larger than the tympanic membrane will then be placed against the lateral surface of the tympanic membrane to completely covered it. For the placebo group, only sterile water will be delivered by the pharmacy for saturation of the gelatin sponge.
- 4) The pledget will be secured in place with several drops of fibrin glue (Tisseel, McKesson Health Solutions, Auburndale, MA).
- 5) After the effects of the topical anesthetic have worn off, if any, the patient will be released with the following instructions:
 - a) Avoid violently sniffling or blowing the nose
 - b) Sneeze and cough naturally through the mouth without occluding the mouth with the hand.
 - c) Use cotton balls covered with petroleum jelly on the outer surface when washing the hair and bathing, to keep water out of the ear.
 - d) Avoid using a hearing aid in the treated ear.
 - e) Avoid flying, using elevators in tall buildings, and other situations involving substantial changes in air pressure.
 - f) Avoid swimming.
- 6) The subject will then come back at three weeks (+/- 7 days) for a follow- up appointment. The tympanic membrane will be examined to see if the perforation has closed and photographed in the same fashion as during the IMP or initial administration visit. Additional otologic tests will be performed during this follow up exam as well (See 13.1 Schedule of Assessments). If the tympanic

membrane has closed, then the participant will be seen again in approximately 2 months (+/- 7 days) for a final study visit.

However, if the perforation has not closed, then the FGF-2 or placebo application will be duplicated in the same fashion at this follow up visit. The subject will then be seen again at three weeks (+/- 7 days). The tympanic membrane will be assessed again. If the TMP is not healed, then a third application of the FGF-2 or placebo will be applied again at this visit. Additional otologic tests will be performed once again. If the TMP heals, then the subject will be seen again following this visit, or at approximately two months (+/- 7 days).

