Once the subject completes Visit 1, Visit 2, and Visit 3, the subject will come back for Visit 4 (+/- 7 days). During this visit, the perforation will be examined again. If the perforation has not closed completely at this visit, then the blind on the subject's randomization status will be broken. If the subject was randomized to placebo, s/he will be crossed over to receive unblinded FGG-2 treatment. If the subject was randomized to FGF-2 treatment, s/he will receive no further study treatment and return in two months (+/- 7 days) for the final follow up visit.

If crossed-over to unblinded FGF-2 treatment, the subject may be given up to three additional treatments. The follow up visits will occur three weeks (+/- 7 days) and the same otologic procedures will be conducted as mentioned before (See Section 13.1, Schedule of Assessments). If the perforation is found to be closed during these visits or when the subject has completed the maximum number of study visits without perforation closure, then the subject will report in 2 months (+/- 7 days) for a final visit. The study will be completed for reporting purposes after all subjects have completed the 2 month (+/- 7 days) follow up final visit.

6. Discussion of Study Design

The investigator and the subject will be blinded to treatment assignment during the Randomized Treatment phase. Subjects whose perforations fail to close during the randomized treatment phase will crossover to the Unblinded Crossover Phase. During the crossover phase, only those subjects who failed placebo will receive unblinded FGF-2 treatment. The rationale for using a dose of 20 μ g in 0.2ml is based on the maximum effective dosages as reported in humans of TMR closure with FGF-2 (Kanemaru et al., 2011).

The subjects, physician, and other study staff members will remain blinded to the treatment arm during the randomized treatment phase as the pharmacy will oversee the randomization process. During the Randomized Treatment phase, the pharmacy will provide the appropriately blinded vial of either FGF-2 or placebo solution as needed upon the request from the physician. Only those subjects who fail the randomized treatment phase will crossover into the unblinded crossover phase. Documentation of the cross-over will be made in the Case Report Forms as well as in the randomization log managed centrally by the dispensing pharmacy.

7. Selection of Study Population

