14.3 Visit 2, Day 22 (\pm 7 Days)

The following procedures will be performed:

- Study drug administration - *if the TMP is not completely closed*
- Vital Signs
- Review of Prior/ Concomitant medication(s)
- TM photography
- Audiogram
- Assessment of Possible Adverse events

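### Section 7.3 starts the ear-complication stop only after three failed treatments, the synopsis after the first; read alone, 7.3 covers no re-dosing in the randomized phase

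*Combined protocol and SAP*

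**What the plan says.** The stop for ear complications appears twice.

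- Synopsis, Discontinuation from Treatment: "If the first treatment does not result in complete closure, subsequent treatments will not be administered if any ear complications occur".
- Section 7.3: "If three treatments do not result in complete closure, subsequent treatments will not be administered if any ear complications occur".

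Both name infection, moderate to severe pain and moderate to severe irritation. The synopsis ends its list with "or clinically significant sensorineural hearing loss". Section 7.3 names clinically significant hearing loss of any type and adds the need for other surgery. A stopped subject stays in the study: "All subjects will complete all safety follow-up visits" (7.3).

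Section 5.1 limits Part A to three applications per subject. If the perforation is still open at Visit 4 the blind is broken. Placebo subjects may then have up to three FGF-2 applications in Part B. For the other arm: "If the subject was randomized to FGF-2 treatment, s/he will receive no further study treatment".

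On re-dosing in Part A, Section 5.1 says that if the perforation is open, "then the FGF-2 or placebo application will be duplicated in the same fashion at this follow up visit". The drug-administration line for Visit 2 in Section 14 carries the condition "if the TMP is not completely closed"; Visit 3 has the same condition, and footnote 4 of Section 13.1 says the same in other words.

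**The concern.** This rule protects participants, and the protocol defines it in two incompatible ways. Section 7.3 is where staff would look for the rule on stopping treatment, and its version starts too late to affect any repeat dose in the randomized phase. The visit instructions do not repair this, because they name only an open perforation as the condition.

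Section 26 describes two sites. A site working from the synopsis would have to stop after, say, moderate pain following the first application. A site working from 7.3 and the visit schedule would have no mandatory rule to stop. The same event could end treatment at one site and not at the other, and treatment stops could not be counted consistently. Section 17.2 restricts the primary efficacy population to subjects without important protocol deviations, so the conflict could also affect who is analysed: whether such a re-dose is a deviation depends on which text governs.

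**Working it through.** The plan states no figure on this point. The check compares texts and counts which dosing decisions each version reaches.

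**Inputs.** Maximum applications in Part A: 3 (synopsis; 5.1). Further applications after three failures: none for FGF-2, up to 3 for placebo (5.1). Arm sizes: 45 FGF-2 and 15 placebo (synopsis, Statistical Analysis); the synopsis also plans 75 subjects in all.

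**Step 1. Decisions per subject.** Re-dosing decisions in Part A = 3 − 1 = 2, for applications 2 and 3.

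| Decision | Who faces it | Failed treatments so far | Synopsis stop applies | 7.3 read alone applies |
|---|---|---|---|---|
| Application 2 | both arms | 1 | yes | no |
| Application 3 | both arms | 2 | yes | no |
| Applications 4 to 6 | placebo crossovers only | 3 or more | yes | yes |

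For a subject randomized to FGF-2, 7.3 reaches 0 of 2 decisions. For a placebo subject it reaches at most 3 of 5.

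**Step 2. Trial-level upper bound,** assuming that no ear closes and nobody drops out.
- Part A: (45 + 15) × 2 = 120 decisions, of which 45 × 2 = 90 are in the FGF-2 arm. Section 7.3 covers none of the 120.
- Part B: 15 × 3 = 45, all covered by 7.3.
- Total: 120 + 45 = 165. Section 7.3 covers 45/165 = 27%; the synopsis covers all 165.
- With 75 subjects, Part A has 75 × 2 = 150 decisions, again none covered by 7.3.

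These counts show the reach of the wording. They do not estimate harm, and the real number of decisions falls with every ear that closes early.

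**Step 3. What else applies before a repeat dose in Part A.**
- Infection or inflammation: the first step of the procedure in 5.1 confirms "that no active infection and/or inflammation is present". If repeating the application in the same way includes that step, the check recurs.
- Hearing: footnote 1 of 13.1 puts audiology before dosing, but no visit instruction says to withhold the dose on the result.
- Pain and irritation: adverse events are asked about at every visit (15.1), but no visit instruction links the answer to the dose.
- Section 7.4 lists adverse events among potential reasons for removal from treatment, without criteria.

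**Step 4. Section 18.** Its review of study progression by the Data and Safety Monitoring Board (DSMB) is timed to the start of later dose-escalated cohorts. Sections 5.1 and 8.1 give one FGF-2 concentration, 100 µg/mL, so that point cannot occur.

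**The case against.** The best defence is that the stop is in force. The synopsis belongs to the same protocol, and obeying it never breaches 7.3, which nowhere authorises re-dosing an ear with a complication and introduces its reasons as a non-exhaustive list. On this view 7.3 contains a drafting slip. That may well be how it arose, but it leaves the two texts in conflict in the section on removal from treatment.

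Some stronger readings are tempting and should not be drawn:

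- *Part A has no protection.* The synopsis stop, Section 7.4 and the repeated infection check say otherwise.
- *Re-dosing follows automatically from an open perforation.* The synopsis says treatment may be repeated as needed, and Section 6 has the pharmacy supply each vial when the physician asks. Both leave discretion, although 5.1 and footnote 4 are more directive.
- *Adverse events are reviewed only after dosing, because the visit lists put them last.* The lists for Visits 2 and 3 put drug administration ahead of the photography and audiogram that must precede it, so they are not a sequence. The schedule table is not clear enough to support an argument from a missing footnote mark.
- *The safety board has no working review, or never hears of non-serious stops.* Section 18 refers to periodic reviews in a charter that is not among the documents, and Section 16.2 has the safety committee monitor completed case report forms. Early notice of every treatment stop would be a preference, not a correction.
- *The counts measure risk.* They contain no complication rate, and Section 3.2 reports no serious sequelae in the human study of this gelatin-sponge and fibrin-glue method.

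**Conclusion.** The inconsistency stands and should be corrected. Taken alone, 7.3 covers 0 of 2 Part A re-dosing decisions per subject and can never bind for anyone randomized to FGF-2; the synopsis covers both decisions. The complication lists disagree on hearing loss and on other surgery. The existing protections are real but partial: moderate to severe pain, irritation and hearing loss have no explicit mandatory stop outside the synopsis until three treatments have failed.

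The conclusion rests on reading 7.3 literally and on the three-application limit in 5.1. It assumes no complication rate, and it does not show that any subject would in fact be re-dosed wrongly. Sample size, power and alpha are unaffected. The dose-cohort sentence in Section 18 is a secondary wording fault; how much it matters depends on the charter.

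**What to change.** 1. Reword 7.3: *After any application, including the first, in Part A or Part B, no further study treatment is given if an ear complication occurs in the treated ear.* Use one list of complications in 7.3 and the synopsis, and state whether any clinically significant hearing loss counts or only sensorineural loss.
2. Add *and no 7.3 ear complication has occurred* to footnote 4 of Section 13.1 and to the drug-administration lines in Section 14 for Visits 2 to 6.
3. As a minor correction in Section 18, replace the dose-cohort review point with a DSMB review at the n = 30 interim analysis already planned in 17.5 and at other times set in the charter. If the charter already sets review times, this changes wording only.

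The cost is text edits. No new data are needed, since adverse events are already recorded at every visit, and the stop itself is already in the synopsis. Applying it does have a price. The synopsis counts a discontinued subject as not improved, so with 45 and 15 subjects analysed each stop lowers observed closure by at most 1/45 = 2.2 percentage points for FGF-2 or 1/15 = 6.7 points for placebo. A placebo subject stopped in Part A also does not cross over, which slightly shrinks the sample for the salvage rate.

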7.4 Premature Termination

Potential reasons for removal of subjects from treatment include the following:

- Withdrawal of consent
- Adverse Events
- Patient is lost to follow-up
- Termination of study by the Sponsor
- Pregnancy

8. Treatments

8.1 Identity of Investigational Product(s)

FGF-2 is manufactured by Kaken Pharmaceutical Co., Ltd. and will be supplied by Nobelpharma Co Ltd.

The FGF-2 method of use comprises a pledge of gelatin sponge, with human fibroblast growth factor-2 (FGF-2) added to the pledge just before topical application to the tympanic membrane, and the use of fibrin glue used for applications in ear surgery. The concentration of the FGF-2 solution will be 100 μ g of FGF-2 per 1 mL with an estimated dose of about 20 μ g in 0.2mL.

9. Handling and Disposition of Study Drug

9.1 Packaging and Labeling

All packaging and labeling operations will be performed according to the requirements of Directive 2001/20/EC¹ and in accordance with Good Manufacturing Practice for Medicinal Products.

9. Conditions for Storage and Use

FGF-2 is to be stored in a cool location. The expiration date is as indicated on outer box and label. After reconstituting, FGF-2 is to be kept in a cool, dark place at $\leq 10^{\circ}\text{C}$ and used within weeks. In this clinical study, the product will be prepared as needed, with 1 vial used for each case in this clinical study.

10.1 Instructions to the Pharmacist

Lyophilized FGF-2 in the amount of 250 μ g will be supplied in vials along with 2.5 ml of sterile water to the clinical site pharmacy for preparing dosing levels at 10 μ g/mL. The drug kits will also provide dilution instructions to the pharmacist. The control solution will consist of the sterile water without any FGF-2.

Fibrinogen tissue glue will be supplied in 4 vials to the pharmacist. The first powdered fibrinogen (vial 1) is reconstituted with all of the aprotinin solution (vial 2) to prepare Solution A. The thrombin powder (vial 3) is reconstituted with a volume of calcium chloride solution (vial 4) equal to the volume of the aprotinin solution to prepare solution B. Several drops of solution A and then solution B are applied in layers to the lateral surface of the gelatin sponge in the medial external auditory canal at the site of the adhesion.

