- If female, post-menopausal, sterile, or if she is of child-bearing potential, she must have a negative beta-HCG test and must agree to use an adequate form of birth control throughout the clinical trial.

Key exclusion criteria:

- Active otitis media or chronic otorrhea from the middle ear
- Subjects receiving radiation therapy, corticosteroids, immunosuppressive agents, or chemotherapy
- Subjects who, at study entry, are taking systemic antibiotics
- Subjects who are immunosuppressed
- Subjects experiencing bacterial or viral infection or who may otherwise be febrile
- Life expectancy of less than 1 year
- Active alcohol or drug abuse within 6 months prior to study entry
- Significant medical condition that could prevent full participation in the procedures required for the study (see Section 7.2 for full list of exclusions)
- Known or suspected allergies to any components used in the study, i.e. porcine collagen
- Subjects who have cholesteatoma mass in the tympanic cavity
- Subjects whose total perforation cannot be seen by an endoscope
- Subjects with inadequately controlled diabetes mellitus (NGSP: HbA1c 6.9% or higher)
- Subjects with a history of malignant ear canal tumors within 3 years of screening for eligibility

TEST PRODUCT, DOSE, AND MODE OF ADMINISTRATION:

Subjects will receive an estimated 0.2 mL of 100 µg/mL of FGF-2. The FGF-2 will be mixed from 250 µg (300,000 international units) of lyophilized FGF-2 with 2.5 ml of sterile water. After saturation of the gelatin sponge, it is estimated that the gelatin sponge will contain approximately 20 µg in 0.2 ml of the solution. The actual size of the pledget may vary slightly depending upon the size and configuration of the perforation. The application of the FGF-2 will proceed according to the following protocol. The fibrin glue consists of human fibrinogen, human blood coagulation factor XIII, aprotinin solution, thrombin, and calcium chloride hydrate.

- 1) In an outpatient examination, confirm that the patient has a tympanic membrane perforation and no active infection/inflammation is present, then insert a cotton ball soaked in 2% lidocaine jelly directly to the surface of the tympanic membrane under the microscopic visualization.

- 2) After 15 minutes, the lidocaine infused cotton ball will be removed and the edge of the perforation roughened with a micropick to remove the epithelium circumferentially around the perforation edge.

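### Section 10.1 gives the pharmacist a target of 10 µg/mL, but its own 250 µg in 2.5 mL makes 100 µg/mL, the concentration stated everywhere else

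*Combined protocol and SAP*

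**What the plan says.** Section 10.1 (Instructions to the Pharmacist) supplies 250 µg of lyophilized FGF-2 "in vials along with 2.5 ml of sterile water to the clinical site pharmacy for preparing dosing levels at 10" µg/mL. It adds that the kits carry dilution instructions, and it defines the control as sterile water alone. It repeats neither the 20 µg dose nor the 0.2 mL volume.

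The other statements of concentration and dose are:

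- **Synopsis (test product and dose):** "Subjects will receive an estimated 0.2 mL of 100" µg/mL, made by mixing 250 µg "of lyophilized FGF-2 with 2.5 ml of sterile water", so that the sponge holds about 20 µg in 0.2 mL.
- **Section 5.1, design:** "The OBD was determined to be 100" µg per mL, with about 20 µg in 0.2 mL.
- **Section 5.1, application steps:** an FGF-2 "soaked pledget (approximately 20" µg in 0.2 mL).
- **Section 6:** "The rationale for using a dose of 20" µg in 0.2 mL is taken from earlier human experience.
- **Section 8.1:** "The concentration of the FGF-2 solution will be 100" µg per mL, again with about 20 µg in 0.2 mL.

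**The concern.** Section 10.1 is addressed to the person who prepares the drug, and 10 µg/mL is the only concentration it states. That figure disagrees by a factor of ten with the two quantities in the same sentence and with the rest of the protocol. The mention of kit dilution instructions could make a further dilution step look intended.

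If someone prepared to the stated target, the active arm would receive a tenth of the dose the trial sets out to test. The primary objective is closure against placebo at the chosen dose, so a failure to show benefit could then reflect under-dosing rather than a lack of effect. The documents give no human closure rate at 2 µg, so the loss of efficacy cannot be put into numbers.

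The usual clinical checks might not reveal such an error. Section 6 says: "The subjects, physician, and other study staff members will remain blinded to the treatment arm during the randomized treatment phase". They receive a blinded vial from the pharmacy, so the check on concentration rests mainly with whoever prepares it.

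**Working it through.** **Inputs**

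| Quantity | Value | Source |
|---|---|---|
| FGF-2 per vial | 250 µg | Section 10.1; synopsis |
| Sterile water | 2.5 mL | Section 10.1; synopsis |
| Preparation target | 10 µg/mL | Section 10.1 |
| Concentration | 100 µg/mL | Synopsis; Sections 5.1 and 8.1 |
| Volume per application | about 0.2 mL | Synopsis; Sections 5.1, 6 and 8.1 |
| Dose per application | about 20 µg | Synopsis; Sections 5.1, 6 and 8.1 |
| Maximum applications in the randomized phase | 3 | Synopsis; Section 5.1 |

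**1. Try to reproduce the Section 10.1 figure.** Concentration = mass / volume = 250 / 2.5 = 100 µg/mL. The stated 10 µg/mL is not reproduced; the ratio is 100 / 10 = 10.

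**2. Reproduce the figure used elsewhere.** Dose = concentration × volume = 100 × 0.2 = 20 µg. Working back, 20 / 0.2 = 100 µg/mL. The synopsis and Sections 5.1, 6 and 8.1 all fit together.

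**3. Look for a reading that makes 10 µg/mL correct.**

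- *Dilute the whole vial further.* Total volume = 250 / 10 = 25 mL, which is 25 − 2.5 = 22.5 mL more than Section 10.1 supplies. No section describes this step.
- *Keep 2.5 mL and change the mass.* Mass = 10 × 2.5 = 25 µg, a tenth of the vial content.
- *Keep the 20 µg dose.* Volume = 20 / 10 = 2 mL on the sponge, ten times the stated 0.2 mL.

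Diluting only part of the vial could also reach 10 µg/mL, but nothing in the protocol describes that, and it would not restore the 20 µg dose.

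**4. Consequence of each preparation**, taking 0.2 mL per application and three applications:

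| Preparation | Concentration | Per application | Three applications |
|---|---|---|---|
| Use the supplied 2.5 mL | 100 µg/mL | 0.2 × 100 = 20 µg | 3 × 20 = 60 µg |
| Follow the stated target | 10 µg/mL | 0.2 × 10 = 2 µg | 3 × 2 = 6 µg |

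The 0.2 mL is the protocol's estimate, and the synopsis allows pledget size to vary. The absolute doses would move with it; the tenfold ratio would not.

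**The case against.** The other side concedes the arithmetic but questions whether the protocol itself is wrong and whether anyone would be misled.

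**A lost digit.** The text was read from PDF, and the storage section just before Section 10.1 gives a use-by period in weeks with no number. A numeral therefore appears to be missing nearby, whether by omission or in reading, and 100 could have become 10. This cannot be excluded. Against it, the 250 and 2.5 in the same sentence came through, as did 100 in the synopsis and Sections 5.1 and 8.1. There is also a plausible origin in the document. Section 10.1 speaks of dosing levels in the plural, Section 18 refers to dose-escalated cohorts, and Section 13.2 points to Section 7.1 for a dose-limiting-toxicity definition that is not there. This suggests text left over from a dose-escalation design, but does not prove it. The source page settles the matter.

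**Little practical risk.** Using the materials as supplied gives the right concentration. Under-dosing requires someone to follow the target over the supplied volume and to miss the synopsis and Section 8.1. The pharmacy may work mainly from the kit instructions, which are not in the documents. All of this stands; it limits the likelihood of harm but does not make the figure right.

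**Blinding adds little.** Section 6 blinds staff to treatment arm; that they would not notice a weak solution is an inference, and the crossover phase is unblinded. Section 10.2 makes clear that the pharmacist at the main site knows the assignment, but for the second site it says only that designated staff receive it, not who prepares the drug. These points are fair, and neither bears on the contradiction or its correction.

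**Conclusion.** The concern holds. As the text stands, the preparation target in Section 10.1 is a tenth of what its own quantities produce and a tenth of the concentration given in the synopsis and Sections 5.1 and 8.1. The intended value is clearly 100 µg/mL.

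The conclusion about the figure rests on the documents and simple division. The consequence is conditional: 2 µg rather than 20 µg per application, and only if the stated target is followed instead of the supplied volume. No such preparation has been shown, and whether the kit instructions repeat the wrong figure is unknown. One reservation remains, that the digit may have been lost in reading the PDF. The point changes no endpoint, sample size or analysis. It should still be fixed, because it sits in the operative instruction for preparing the drug.

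**What to change.** 1. Look at the source page of Section 10.1. If it already reads 100 µg/mL, no protocol change is needed.
2. If it reads 10 µg/mL, change the figure to 100 µg/mL. It would help to state the arithmetic there too: 250 µg in 2.5 mL gives 100 µg/mL, about 20 µg per 0.2 mL application.
3. Before any dispensing, confirm that the dilution instructions in the kits say the same, and that whoever prepares the drug at each site has the corrected text.

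The cost is a one-figure protocol correction and one check of the kit instructions.
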